11.4. LABORATORY EVALUATIONS

Blood and urine samples for hematology, clinical chemistry, and urinalysis (referred to collectively as safety laboratory data) will be collected according to the Time and Events Schedule (Table 2).

The following tests are included:

- **Clinical Chemistry:** alkaline phosphatase (ALP), calcium, chloride, creatinine, random glucose, potassium, alanine aminotransferase (ALT), aspartate

aminotransferase (AST), gamma-glutamyl transpeptidase, sodium, total bilirubin, and urea.

- **Hematology:** A peripheral blood smear to assess blood cell morphology, hemoglobin, hematocrit, red blood cell (RBC) count, white blood cell (WBC) count, WBC differential (absolute counts), and numerical platelet count.
- **Urinalysis:** specific gravity, pH, ketones, random glucose, nitrite, blood, leukocyte esterase, protein, urobilinogen, and bilirubin. If nitrite, blood, or protein tests are positive, a microscopic examination will be performed.
- **Pregnancy:** presence of B-Human Chorionic Gonadotropin (HCG) in the blood serum or urine of all female subjects. Results of blood serum and urine pregnancy tests will be reported and determined to be negative prior to study continuation and/or dosing.
- **Follicle-Stimulating Hormone (FSH):** Post-menopausal status for female subjects will be confirmed by FSH testing at Screening.
- **Viral Screen:** Serology will screen for hepatitis B, hepatitis C, and HIV. Only subjects with negative viral serology tests will be eligible for the study.
- **Breath Alcohol:** If there is any doubt or concern regarding alcohol use, research site staff may request a breath alcohol test at any time during the study.
- **Drugs of Abuse Screen:** Urine samples will be tested for the following drugs of abuse: THC, oxycodone and other opiates (i.e., the opiate panel will test for the presence of codeine, hydrocodone, hydromorphone, morphine, and oxymorphone), amphetamines (i.e., amphetamines and methamphetamines), cocaine, and benzodiazepines.

Laboratory data collected during the Dose Selection Phase will be summarized by the type of laboratory test and visit. Descriptive statistics (n, mean, SD, minimum, median and maximum) and the number of subjects with laboratory test results below, within, and above normal ranges will be tabulated by visit.

Continuous laboratory test results will be assigned a low/high/normal (LNH) classification by the central lab according to whether the value was below (L: Low), within (N: Normal), or above (H: High) the laboratory parameter's normal range; categorical laboratory test results were classified as normal (N) or abnormal (A).

Abnormal findings in laboratory data will be listed. Abnormal values, classified as Low/Normal/High (LNH), and clinically significant abnormalities (as determined by the investigator) will be flagged. Laboratory listings will be provided for the Dose Selection Randomized Population.

All laboratory test results will be reported in Standard International System of Units (SI) units.

11.5. VITAL SIGNS

Vital signs consist of systolic and diastolic blood pressure (mmHg), heart rate (beats per minute [bpm]), and respiratory rate (breaths/minute). Oral temperature (°C) will also be taken at some time points according to the Time and Events Schedules (Table [Dose Selection]).

In addition, pulse oximetry measurements (SpO₂) will be taken at designated time points after the continuous monitoring period.

Dose Selection Phase vital signs (blood pressure, respiratory rate, heart rate, SpO₂) will be analyzed as minimum, maximum, and final post-dose (i.e. 24 hours) values and summarized using descriptive statistics (n, mean, SD, minimum, median and maximum), since the analyses of these extremes are more meaningful than the analyses of individual time points. The individual time points and all off-treatment vital signs (i.e., Screening, and Follow-up) will be listed for the Dose Selection Randomized Population but not otherwise analyzed. Abnormal findings in vital signs data will be listed. In the Dose Selection Phase, baseline will be determined as the last observed measurement prior to the administration of study drug. In addition, minimum, maximum, and final post-dose individual values will be derived and individual data will be presented in data listings.

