The median  $T_{max}$  of nalbuphine is expected to occur between 0.5 and 1.5 hours post-dose after oral administration of nalbuphine solution, while the median  $T_{max}$  is expected to occur between 3 and 6 hours post-dose after nalbuphine ER tablets. The PK sampling in the Treatment Phase was developed to capture the expected  $T_{max}$  of nalbuphine of both nalbuphine formulations. The mean  $T_{max}$  for orally-administered hydromorphone HCl solution is expected to occur at approximately 0.7 hours. In addition, the  $t_{1/2}$  of nalbuphine ranges from 6.6-9.6 hours, whereas the  $t_{1/2}$  for hydromorphone is approximately 2.3 hours. Based on this, a 24-hour assessment period and 24-hour post-dose discharge for each treatment visit is considered safe for the subjects, and at this time the PD measures are expected to return to approximately baseline. A minimum 4-day washout between each dose in the Treatment Phase is considered acceptable based on the  $t_{1/2}$  of the active agents to be used in this study, as it is a duration that is longer than five times the maximum  $t_{1/2}$  of the longest acting drug in the study, as recommended in the FDA guidance.

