### 6.3.5 Vital Signs

Vital signs will be measured after subjects have been at rest for approximately 3 minutes at the time points specified in the Schedule of Events. Vital signs will consist of systolic and diastolic blood pressure (mmHg), heart rate (bpm), and respiratory rate (breaths/min). Oral temperature (°C) will also be taken at some time points. In addition, pulse oximetry measurements will be taken with the vital signs monitoring system (eg, Dinamap) at designated time points and recorded after the continuous monitoring period (Section 6.3.6).

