### 6.3.6 Continuous Pulse Oximetry

Continuous pulse oximetry will be performed by telemetry from pre-dose until at least 4 hours post-dose during the Qualification Phase in Part B and at least 6 hours post-dose during the Dose Selection Phase in Part A and the Treatment Phase in Part B, or longer, based on the discretion of the investigator or designee.

Continuous monitoring will include real-time measurements of SpO2. Oxygen saturation readings will be recorded at designated time points. After the continuous monitoring period, pulse oximetry measurements will be taken with the vital signs monitoring system (eg, Dinamap) at designated time points and recorded.

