The dose escalation scheme in Part A was amended to allow an incremental increase in the dose of nalbuphine based on a percentage of up to 50% from the last dose (rather than an absolute 27 mg dose increase), if supported by the safety data of the preceding cohorts.

The amendment is proposed based on the safety results of the first 4 cohorts indicating a lower than expected incidence of AEs and severity up to the 162 mg nalbuphine. Data indicated that - unlike healthy subjects- nalbuphine is much better tolerated in the non-dependent recreational opioid population and that the dose-AE response was flat over the selected dose range. At the 162 mg therapeutic dose (Cohort 4) only one Grade 2 AE was observed out of a total of 14 AEs. Subjects dosed at 81 mg had very mild AEs (2 out of 6 subjects had Grade 1 somnolence) with no nausea or vomiting compared to 5.9% in healthy subjects. Grade 1 vomiting and nausea were observed in one subject out of 6 at 135 mg while doubling the dose from 81 mg to 162 mg resulted in a single AE of Grade 2 nausea reported in one out of 6 drug treated subjects. This is in contrast to the observed incidence of vomiting (32%), nausea (41%) AEs in healthy subjects at the 162 mg dose. There was no effect on oxygen saturation ( $spO_2 > 95\%$ ), ECG parameters, or any other vital signs over 24 hours post-dose in any individual subject up to 162 mg dose.

In view of the “flat” dose-response observed in this subject population, the protocol was amended to allow an incremental increase in the dose of nalbuphine based on a percentage of up to 50% from the previous dose (rather than an absolute 27 mg dose increase). The 50% increase was selected to ensure a sufficient differentiation between the doses while keeping in perspective the potential safety of the subjects as the doses are escalated to the higher doses. Given the high inter-subject variability of 54% in nalbuphine plasma  $C_{max}$  and 46% in AUC, a 50% increase seemed further justified.

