Serum Pregnancy	X	X															
Urine Pregnancy		X															
FSH (postmenopausal women)	X																
HIV, Hepatitis B, Hepatitis C	X																

^a Focusing on any changes since the last visit.

^b Symptom-directed physical examination

	Screening Visit	Dose Selection Phase																			
		Naloxone Challenge	Dose Selection Cohorts																		
Visit:	1	2																			
Day:	-30 to -2	-1	1													2					
Assessment time points relative to dosing (hours)																					
			Pre				1		2		3	4	5	6		7	8	10	12	24	
Vital Signs ^c	X	X ^d																			24
Oral Temperature	X	X																			24
Electrocardiogram	X	X																			24
Urine Drug Screen	X	X																			
Breath Alcohol	X	X																			
Continuous Pulse Oximetry ^e			Predose until at least 6 hours post-dose																		
Clinical Laboratory Tests	X																				24
Concomitant Medications			< -- recorded throughout -- >																		
Adverse Event Monitoring ^f	X	X	< -- recorded throughout -- >																		
COWS		X																			
Pharmacokinetics																					
Nalbuphine			Pre	0.25	0.5	1	1.5	2	2.5	3	4	5	6			8	10	12	24		
Pharmacodynamics																					
Pupillometry			Pre	0.25	0.5	1	1.5	2	2.5	3	4	5	6			8	10	12	24		
Study Administration																					
Naloxone Administration		X ^g																			
Randomization			pre ^h																		
Admission		X																			

^c Vital signs will include blood pressure, heartrate, and respiratory rate. Vital signs will also include measurements of oxygen saturation after continuous pulse oximetry monitoring is complete.

^d Pre-naloxone challenge and at 10 minutes and 1 hour post-naloxone challenge, as indicated in Section 4.4 of the Protocol.

^e Oxygen saturation will be monitored continuously via telemetry for at least 6 hours post-dose or longer, if deemed necessary by the investigator or designee to ensure subject safety.

^f Spontaneous AE reporting is continuous throughout the study; however, AE questioning may be performed using a non-leading question at discretion of the clinical staff.

^g Naloxone challenge procedures are described in Section 4.4 of the Protocol. For female subjects, the results of the urine pregnancy test are required prior to the naloxone challenge; results of the serum pregnancy test will not be required prior to the naloxone challenge.

^h Day 1 only.

	Screening Visit	Dose Selection Phase													

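### Does the SpO2 minimum in SAP 11.5 leave out the hours around peak nalbuphine exposure?

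*SAP*

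**What the plan says.** SpO2 is one of the vital signs named as a safety endpoint in SAP 4.1.2. SAP 11.5 lists blood pressure, heart rate and respiratory rate, and adds that pulse oximetry measurements "will be taken at designated time points after the continuous monitoring period". It then states that the Dose Selection Phase vital signs, SpO2 among them, "will be analyzed as minimum, maximum, and final post-dose (i.e. 24 hours) values and summarized using descriptive statistics".

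SAP Table 2 (Section 3.7) schedules continuous oximetry as "Predose until at least 6 hours post-dose". Footnote c to that table reads: "Vital signs will also include measurements of oxygen saturation after continuous pulse oximetry monitoring is complete".

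Protocol 6.3.5 uses similar wording: oximetry with the vital-signs system is taken "at designated time points and recorded after the continuous monitoring period". Protocol 6.3.6 describes continuous telemetry and, before it turns to the later spot readings, adds: "Oxygen saturation readings will be recorded at designated time points".

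The SAP indexes list one vital-signs summary (Table 14.3.4.2.1), one abnormal-results listing (14.3.4.2.2) and one data listing (16.2.8.2.1). There is no separate oximetry output.

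**The concern.** Protocol 3.2.2 says that the median Tmax "is expected to occur between 0.5 and 1.5 hours post-dose after oral administration of nalbuphine solution". The only SpO2 readings SAP 11.5 mentions begin once continuous monitoring ends, at 6 hours or later. A programmer who took that sentence and footnote c as the source rule would compute a post-dose minimum with nothing from the hours of highest exposure. For an opioid those are the hours of most interest, and SAP 11.5 chooses extremes because it regards them as more informative than single time points. A minimum taken over fewer and later readings can only be equal to or higher than one taken over all readings, so any error would make the by-dose SpO2 summary look more favourable. Neither SAP 7.1 nor Protocol 8.1.5 says which readings enter the minimum.

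**Working it through.** **Time points on the literal reading.** The scheduled post-dose vital-sign times in Part A (Protocol Table 1, SAP Table 2) are 1, 2, 3, 4, 5, 6, 7, 8, 10, 12 and 24 hours, 11 in all.

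- After 6 hours: 7, 8, 10, 12, 24, so 5 of 11 (5/11 = 45%).
- Counting a reading at 6 hours when monitoring stops: 6 of 11 (6/11 = 55%).
- From 1 to 5 hours: 5 scheduled times, none of which would supply SpO2.
- Gap between expected Tmax and the earliest such reading: 6 − 1.5 = 4.5 hours to 6 − 0.5 = 5.5 hours.
- Scheduled vital-sign times inside the 0.5 to 1.5 hour window: one (1 hour).

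**Whether the text supports that reading.** Four comparisons bear on it.

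1. *Collection against derivation.* Protocol 6.3.5 and 6.3.6 show why the phrase about the end of monitoring is there: SpO2 comes first from telemetry and then from the vital-signs monitor. The SAP sentence marks that change of device. The derivation sentence is separate. It treats SpO2 exactly like blood pressure, heart rate and respiratory rate, and its only time qualifier is post-dose.
2. *No word of exclusion.* Neither SAP 11.5 nor footnote c says that only the later readings count. Footnote c adds a measurement to the vital-signs set and removes none.
3. *Baseline.* SAP 11.5 defines the vital-sign baseline as the last measurement before dosing. Continuous oximetry starts before dosing. If SpO2 counted only after monitoring ended, there would be no pre-dose SpO2 on the dosing day, so the literal reading sits badly with the section's own baseline rule.
4. *The sponsor's own use of the data.* The rationale in Protocol 12.2 states that SpO2 stayed above 95%, with no effect on it "or any other vital signs over 24 hours post-dose in any individual subject up to 162 mg dose". SpO2 is grouped there with the other vital signs and described over the whole 24 hours. That is hard to square with a source that starts at 6 hours.

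**Doses not covered by that statement.** It reaches 162 mg, the first four dose levels. SAP 3.2 gives five planned cohorts, which leaves one level above it (243 mg). SAP Table 1 gives seven, which leaves three (243, up to 365 and up to 486 mg). The documents do not show that cohorts 6 and 7 were dosed.

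**What depends on the answer.** Each cohort has 6 active and 2 placebo subjects. The affected outputs are descriptive, with no hypothesis test. Escalation rested with the Data Review Committee, which reviewed unblinded safety data after each cohort (Protocol 4.9), and SAP Section 5 records that Part A is complete. Adverse events are tabulated separately, and respiratory rate is scheduled from 1 hour and has its own minimum.

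A difference in SpO2 points cannot be derived from the documents, because it needs an assumed early fall in saturation and they report none.

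**The case for a change.** The best case for acting is that two careful programmers could produce different safety minima from the same SAP. One follows SAP 11.5 and footnote c and drops the early readings. The other follows Protocol 6.3.6 and keeps them. Preventing that is part of what a SAP is for. The cohorts were unblinded as Part A went along, so a rule left to programming is a rule chosen after results are known. A clarifying sentence would cost almost nothing.

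Part of this stands. The SAP does not state the rule. The mock tables are a separate attachment not among the documents, so they cannot be cited as settling it. The Protocol 12.2 statement supports the full-record reading but does not list its reading times. Using all readings also mixes telemetry with spot measurements, and subjects monitored for longer may contribute more values.

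What does not stand is the step from an unstated rule to a likely exclusion. To drop the early values, a programmer would have to discard recorded post-dose SpO2 data on the strength of a sentence about when a different device is used, and would lose the dosing-day baseline as well. That is the less natural course.

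**Conclusion.** No change to the plan is called for. SAP 11.5 leaves a small detail unstated, and analysts would fill it sensibly by taking minimum, maximum and final SpO2 from all recorded post-dose readings.

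This rests on two assumptions. The first is that readings during monitoring were recorded as Protocol 6.3.6 requires, at times that include the early vital-sign schedule. The documents do not give those designated times, but the 24-hour statement in Protocol 12.2 supports it. The second is that the unseen table shells do not restrict the source.

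If the literal reading were programmed, SpO2 would come from 5 or 6 of 11 post-dose times and the reported minimum could be too high. That would affect a descriptive by-cohort summary. It would not alter any escalation decision, the maximum safe dose or the adverse-event reporting. The SAP covers Part A only, so nothing here bears on Part B.

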11.6. ECG

12-lead ECGs will be performed by the site according to the Time and Events Schedules (Table [Dose Selection]). The ECG will electronically measure and calculate ventricular heart rate and the PR, QRS, QT, QTcB, and QTcF intervals. ECG data will be classified as “Normal”, “Abnormal, Not Clinically Significant” or “Abnormal, Clinically Significant”.

12-lead ECG data (absolute values in heart rate and PR, QRS, QT, QTcB, and QTcF intervals) will be summarized by parameter and visit using descriptive statistics (n, mean, SD, minimum, median and maximum). Abnormal findings in ECG data will be listed. A summary table of overall ECG interpretation will show the number and percentage of subjects with normal, abnormal non-clinically significant (NCS) or abnormal clinically significant (CS) findings at each visit. ECG data will be listed for the Dose Selection Randomized Population.

11.7. PHYSICAL EXAMINATION

A complete physical examination including general appearance, eye, ear, nose and throat, head and neck, respiratory, cardiovascular, gastrointestinal, musculoskeletal, dermatological, peripheral vascular, lymphatic, neurological, mental status and other body system status, will be performed at Screening. Subsequent symptom-directed physical examinations will be performed according to the Time and Events Schedule (Table 2), and may be performed by physicians or mid-level providers, such as advanced practice nurses and physician assistants, if they are appropriately licensed and credentialed to perform these examinations in accordance with local requirements and/or regulations. Height, weight, and BMI will be recorded at Screening only.

Physical examination abnormal results will be listed by subject and visit for the Dose Selection Randomized Population.

11.8. OTHER SAFETY

Two versions of the Columbia-Suicide Severity Rating Scale (C-SSRS) will be used in this study: the Baseline version to assess lifetime suicidal ideation and behavior at Screening, and the Since Last Visit version to assess suicidal thoughts or behaviors the subject may have had since the last time the C-SSRS was administered.

The Baseline and Since Last Visit C-SSRS results will be listed for the Dose Selection Randomized Population.

11.9. INTERIM ANALYSES

No interim analysis is planned for this trial.

13. PROGRAMMING CONSIDERATIONS

All TLFs and statistical analyses will be generated using SAS® for Windows, Release 9.4 (SAS® Institute Inc., Cary, NC, USA). Computer-generated table, listing and figure output will adhere to the following specifications.

The PK analyses will be performed by Syneos Health using Phoenix WinNonlin® version 6.4 or higher (Certara USA, Inc., Princeton, NJ, USA).

13.1. GENERAL CONSIDERATIONS

- A separate SAS program will be created for each output.
- Each output will be stored in a separate file.
- Output files will be delivered in Word format. TLFs will be bundled separately with a table of contents for each.
- Numbering of TLFs will follow International Council for Harmonisation (ICH E3 guidance)

13.2. TABLE, LISTING, AND FIGURE FORMAT

13.2.1. General

- All TLFs will be produced in landscape format, unless otherwise specified.
- All TLFs will be produced using the Courier New font, size 8.
- The data displays for all TLFs will have a minimum 1-inch margin on all 4 sides.
- Headers and footers for figures will be in Courier New font, size 8.
- Legends will be used for all figures with more than 1 variable, group, or item displayed.
- TLFs will be in black and white (no color), unless otherwise specified
- Specialized text styles, such as bolding, italics, borders, shading, and superscripted and subscripted text, will not be used in the TLFs, unless otherwise specified. On some occasions, superscripts 1, 2, or 3 may be used (see below).
- Only standard keyboard characters will be used in the TLFs. Special characters, such as non-printable control characters, printer-specific, or font-specific characters, will not be used. Hexadecimal-derived characters will be used, where possible, if they are appropriate to help display math symbols (e.g., μ). Certain subscripts and superscripts (e.g., cm², C_{max}) will be employed on a case-by-case basis.
- Mixed case will be used for all titles, footnotes, column headers, and programmer-supplied formats, as appropriate.

13.2.2. Headers

- All output will have the following header at the top left of each page:

Trevi Therapeutics Inc. Protocol TR08 (Syneos Health Study Number 1008910)
Draft/Final Run DMMMMYYYY

- All output will have Page n of N at the top or bottom right corner of each page. TLFs will be internally paginated in relation to the total length (i.e., the page number should appear sequentially as page n of N, where N is the total number of pages in the table).
- The date output was generated will appear along with the program name as a footer on each page.

13.2.3. Display Titles

- Each TLF should be identified by the designation and a numeral. (i.e., Table 14.1.1). A decimal system (x.y and x.y.z) will be used to identify TLFs with related contents. The title is centered. The analysis population will be identified on the line immediately following the title. The title and table designation are single spaced. A solid line spanning the margins will separate the display titles from the Column headers. There will be 1 blank line between the last title and the solid line.

Table x.y.z
First Line of Title
Second Line of Title if Needed
Analysis Population

